complete the Needs Assessment questionnaire over a 2-4 week period at the two time points mentioned above. Where applicable, verbal, written, or electronic consent will be first obtained from legal guardians of residents before obtaining residents' assent and administering the questionnaire to the residents. The content of the questionnaire has been agreed on between MGH researchers and stakeholders. This set of questions is brief (~20 questions) and covers three subject areas: (1) knowledge and reported use of COVID-19 protective practices; (2) vaccine acceptance and (for refusers) reasons for hesitancy/refusal; and (3) mental health, physical health, social support, and vocational secondary impacts of COVID-19. For example, respondents may be asked to select from a list the reasons they declined vaccination. We have worked with stakeholders to adapt the questionnaire so that it is accessible for the ID/DD residents. The ID/DD resident version has now been submitted as an amendment to this protocol. The legal guardian version is abbreviated, containing only questions relating to vaccines. De-identified data from this needs assessment will help to inform refinement of the Tailored Best Practices intervention and will also be provided to the provider organizations to support setting program priorities and planning.

The Needs Assessment questionnaire data will be collected using REDCap or on paper (to accommodate participants' needs). **For those completing the questionnaire on-line**, individual survey links will be e-mailed to the staff, residents, and legal guardians by the provider organizations who will also provide the individual study IDs. Survey responses will be directly submitted back to the MGH research team. **For those completing the questionnaire on paper**, provider organizations will distribute paper copies of the survey and provide the individual study IDs. Deidentified survey responses will be handed or mailed directly to the community research staff at Vinfen for the purposes of providing remuneration. The community research staff at Vinfen will not see any responses, and after remuneration has been provided, they will hand-deliver the deidentified paper surveys to the MGH research team.

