The provider organizations will not have access to the individual responses. No PHI data will be collected. No individual-level data will be shared with the provider organizations, although overall summary statistics across group homes may be shared for quality improvement. Our community partners will assist in the scheduling of online secure Zoom sessions to provide support for questionnaire administration as needed, and they will handle all identifying information for participants. Partners researchers who provide assistance in administering the Needs Assessment questionnaires will do so virtually and will only know the first name of participants. There will be no audio or video recording involved in the questionnaire administration. Participants will receive a \$10 gift card for their participation; community research staff at Vinfen and community-based project managers will distribute the cards to protect identities from the MGH research team. If needed, we will provide tablets to our community partners pre-programmed with the questionnaire.

For (3) the Needs Assessment Questionnaire, all residents and staff will be identified with only a unique, encrypted identifier (detailed below) that will not be linkable with any personal identifiable information by the investigative/research team. Where applicable, all legal guardians will be identified using the unique, encrypted identifier of their ward.

Consistent with hybrid effectiveness-implementation trials, there are co-primary outcomes: a primary effectiveness outcome and a primary implementation outcome.

The primary effectiveness outcome is new COVID-19 group home incidence (new laboratory-confirmed COVID-19 cases among residents and staff). Secondary effectiveness outcomes are rates of hospitalization and mortality.

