The primary implementation outcome is Best Practices Fidelity measured by the COVID-19 Best Practices Fidelity Measure developed for this project and refined with input from stakeholders (uploaded as an attachment to this IRB submission) consisting of fidelity to COVID best practices (e.g., number of staff and residents participating in recommended screening, isolating, contact tracing, PPP protocols, and vaccination interventions by staff and residents of the group homes). Of note, measuring implementation fidelity as the primary outcome provides a test of the effectiveness of TBP vs. GBP independent of the incidence of new cases over the 15-month project if rates of new COVID-19 happen to sharply decline due to temporal trends or a vaccine. Secondary implementation outcomes (informed by the RE-AIM implementation framework) include the following: staff and resident Best Practices Adoption (Acceptability, Appropriateness, and Feasibility Measures); Reach (% of homes using TBPs with 80% fidelity); and Maintenance (% of homes maintaining 80% fidelity over the 15-month study period).

For studies involving treatment or diagnosis, provide information about standard of care at Partners (e.g., BWH, MGH) and indicate how the study procedures differ from standard care. Provide information on available alternative treatments, procedures, or methods of diagnosis.

N/A. This study does not involve treatment or diagnosis.

Describe how risks to subjects are minimized, for example, by using procedures which are consistent with sound research design and which do not unnecessarily expose subjects to risk or by using procedures already being performed on the subject for diagnostic or treatment purposes.

This proposal involves a cluster-randomized trial design where Tailored Best Practices (TBP) and Generic Best Practices (GBP) will be delivered within each agency as part of routine training activities. TBP sites will receive coaching specific to the setting, staff, and residents.

The primary risk is the potential loss of confidentiality. However, we will implement several existing security structures described below to minimize this risk and will only present aggregated data.

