To protect against loss of confidentiality, in all datasets, sites and subjects will be assigned an encrypted study identifier that is distinct from other identifying information. Through identifier and PHI multilayered blinding, data transferred to MGH will thus be deidentified. Each of the 6 provider organizations will be assigned a letter or number series that cannot be used to easily identify them. Vinfen, as a primary collaborating provider organization, will hold the organizational key used to identify each organization. Each provider organization will keep their own key for identifying homes, staff, and residents. For purposes of presentation and publication, data will be presented in aggregate form with no cells with fewer than 10 subjects. All data will be transmitted from the provider organizations to Massachusetts General Hospital using a secure e-mail portal and then stored behind the Massachusetts General Hospital firewall in a password-protected folder on a shared research drive. Data will not be stored on removable devices (e.g., laptops, external drives), and no persons outside of the study team will

have access. In addition to security measures (e.g., password protection of files, encoded identifiers, network firewalls, and locked, magnetic card secured work premises), investigators and staff are required to be CITI certified in Human Subjects Research and sign a confidentiality agreement. Data will be transferred to MGH via secure file transfer or through REDCap. Specifically regarding the Needs Assessment questionnaires, facilities will manage recruitment and MGH researchers will not know the full names of participants.

FORESEEABLE RISKS AND DISCOMFORTS

Provide a brief description of any foreseeable risks and discomforts to subjects. Include those related to drugs/devices/procedures being studied and/or administered/Performed solely for research purposes. In addition, include psychosocial risks, and risks related to privacy and confidentiality. When applicable, describe risks to a developing fetus or nursing infant.

The primary risk to subjects is the potential loss of confidentiality, which we believe is minimal given the security measures we have in place for data transmission.

EXPECTED BENEFITS

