For all resident and staff questionnaires completed on paper: We will provide each group home with a log to track who has completed the questionnaire on paper. This log will have a space for participants to specify how they would like to receive their gift card: via e-mail or in-person. The participant must also provide their contact information (their e-mail address or the physical address of their group home) to receive remuneration. If members of the study team are unable to hand-deliver the paper surveys to the group home, group home staff (who will have been trained to respect residents' autonomy and confidentiality regarding the questionnaire, as described below) will work with residents to assemble a package and send the package to community research staff at Vinfen via postal mail. The package will contain: 1) all completed, de-identified paper questionnaires and 2) a sealed envelope containing the log sheet. Community research staff at Vinfen will keep the sealed envelope containing the log sheet and give the de-identified questionnaires to MGH researchers. This way, no researchers will be able to link the responses to the contact information. If a participant chooses to receive the gift card via e-mail, community research staff at Vinfen and community-based project managers will send an electronic gift card to the provided e-mail address. If a participant chooses to receive the gift card in-person, the community research staff at Vinfen and community-based project managers will deliver a physical gift card to the participant at their group home. If the participant is not present at the time of delivery, the gift card will be delivered in a sealed envelope to the participant's mailbox.

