
We will take a number of precautions to prevent residents with legal guardians from mistakenly completing the survey without guardian consent. We will complete all guardian outreach prior to distributing surveys to residents. After guardian outreach has been completed, each group home will receive a packet that contains: an instruction sheet, a recruitment letter, a fact sheet, surveys, and a log sheet. The log sheet will be preprinted to only include the names of residents who have the necessary consent to complete the survey with a checkbox next to each name to indicate if they completed the survey or not. There will be no spaces on the log sheet to add additional names. This will inform group home staff who can complete the survey and discourage them from adding additional names. The list of names on the log sheet will be verified by two members of the community research staff at Vinfen prior to survey distribution to ensure that only those with the appropriate consent are on the sheet. Each survey will have a cover sheet on which the respondent's name will be preprinted. In the unlikely event that a resident completes the survey without the necessary consent, this will allow us to isolate the survey and retain those completed with the necessary consent. This should also make it extremely clear to group home staff which residents should receive a survey. When possible, community-based project managers and Implementation Coaches will hand deliver these

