packets to the group homes and be present while residents complete the survey, ensuring that only those with the necessary consent receive a survey. They will then collect all surveys and the log sheet in exchange for gift cards (receipts will be signed for gift cards) and deliver them to community research staff Vinfen. If a project manager or Implementation Coach is unable to hand-deliver a packet, they will mail the packet to the group home. Shortly after delivery, the project manager and Implementation Coaches will call the group home's program director to confirm they have received the package, understand the instructions, and know which residents may take the survey. Group home staff will be instructed to use the log sheet to verify which residents are eligible to complete the survey prior to distributing surveys. Group home staff who are less familiar with the residents (e.g., temp staff) will also be instructed to verify the resident's name with the resident prior to giving them the labeled survey. Group home staff will check off the boxes on the log sheet next to the names of the residents who completed the survey. The group home staff will mail the completed surveys and the log sheet directly to the community research staff at Vinfen. Upon receiving the packets, community research staff at Vinfen will look at the cover sheet attached to each survey and verify that the resident had the necessary consent. They will then remove the cover sheet from the survey and hand-deliver the now-deidentified survey to MGH. In the unlikely event that a resident completes the survey without the necessary consent, Vinfen will discard the isolated survey.

Legal Guardian Consent: At the same time that legal guardians are asked to consent to allow their ward to participate in the Needs Assessment, we will also ask the legal guardians to complete a shortened version of the Needs Assessment that focusses exclusively on vaccines. Partners researchers will not have any contact with legal guardian participants, and there is no individually identifiable data collected as part of the questionnaire, so the decision to complete the shortened Needs Assessment questionnaire on vaccines by legal guardians will imply consent.

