The fact sheet will be provided each time the individual is invited to complete the questionnaire and includes the statement that participants can withdraw at any time during the study. During informed consent administration, we shall inform participants that they can refuse to answer any questions and can terminate the questionnaire at any time. All potential participants will be informed that their names and the name of their group home or agency will not be collected and will not be included in any published reports and that their identities will remain confidential with agency and state leadership. Failure to participate in the questionnaire will not affect the services the potential subject receives from DMH and/or DDS or their provider organization now or in the future. Failure to participate in the questionnaire also will not affect any benefits the potential subject receives now or has a right to receive.

NOTE: When subjects are unable to give consent due to age (minors) or impaired decision-making capacity, complete the forms for Research Involving Children as Subjects of Research and/or Research Involving Individuals with Impaired Decision-making Capacity, available on the New Submissions page on the PHRC website:

<http://healthcare.partners.org/phsirb/newapp.htm#Newapp>

For guidance, refer to the following Partners policy:

Informed Consent of Research Subjects

<http://healthcare.partners.org/phsirb/infcons.htm>

DATA AND SAFETY MONITORING

Describe the plan for monitoring the data to ensure the safety of subjects. The plan should include a brief description of (1) the safety and/or efficacy data that will be reviewed; (2) the planned frequency of review; and (3) who will be responsible for this review and for determining whether the research should be altered or stopped. Include a brief description of any stopping rules for the study, when appropriate. Depending upon the risk, size and complexity of the study, the investigator, an expert group, an independent Data and Safety Monitoring Board (DSMB) or others might be assigned primary responsibility for this monitoring activity.

NOTE: Regardless of data and safety monitoring plans by the sponsor or others, the principal investigator is ultimately responsible for protecting the rights, safety, and welfare of subjects under his/her care.

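### The protocol gives two incompatible paper workflows for the resident Needs Assessment; under one, name and answers stay together until Vinfen separates them, and the statement that names are not collected is untrue

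*Protocol*

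**What the plan says.** The protocol describes the handling of paper Needs Assessment questionnaires in several places.

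- **Research Design and Methods (Needs Assessment questionnaire).** Paper responses arrive at Vinfen without identifiers, for remuneration purposes. "The community research staff at Vinfen will not see any responses", and they then carry the forms to the MGH researchers. The section adds: "The provider organizations will not have access to the individual responses".
- **Recruitment Procedures (remuneration, resident and staff paper questionnaires).** When the study team cannot hand-deliver, the mailed package holds "all completed, de-identified paper questionnaires" and, in a separate sealed envelope, the log sheet.
- **Consent Procedures (resident consent).** "Each survey will have a cover sheet on which the respondent's name will be preprinted". Where possible, project managers or Implementation Coaches deliver the packets, stay while residents answer, and collect the surveys and log. Otherwise group home staff mail both. On receipt, Vinfen's community research staff "will look at the cover sheet attached to each survey and verify that the resident had the necessary consent", detach the sheet and deliver the survey to MGH.
- **Consent Procedures (closing paragraph on the fact sheet and participant information).** Potential participants are to be told that "their names and the name of their group home or agency will not be collected".
- **Privacy and Confidentiality.** Respondents' identities are to be known only to community partners recruiting inside their own organizations.

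On risk, Research Design and Methods states: "The primary risk is the potential loss of confidentiality". Foreseeable Risks and Discomforts repeats it: "The primary risk to subjects is the potential loss of confidentiality, which we believe is minimal", and gives the security of data transmission as the reason.

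**The concern.** The questionnaire asks about protective practices, reasons for refusing vaccination, and mental and physical health. The residents who answer depend on the provider organizations for housing and care. A resident told that no names are collected, but handed a form with their name printed on the front, has been given an inaccurate account of how the answers will travel. This happens in a transmission step, and transmission security is the protocol's reason for calling its primary risk minimal.

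There is also a measurement issue. If residents believe that staff can connect them to their answers, some may answer cautiously. The instrument is meant to help refine TBP and to show how individuals experience it, so cautious answers would weaken that use.

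**Working it through.** No arithmetic decides this point. The check sets the two workflows side by side and then tests each assurance against them.

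**The same step, described twice**

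| Feature | Research Design and Recruitment | Consent Procedures (residents) |
|---|---|---|
| Name on the survey | None; de-identified | Preprinted on an attached cover sheet |
| Log sheet | In its own sealed envelope | Preprinted with residents' names; no sealing described |
| State on arrival at Vinfen | Already de-identified | Identified until the cover sheet is removed |
| Sealing of the answers | Not described | Not described |

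Both accounts cover mailing by group home staff when nobody from the study can deliver by hand. A home in that position cannot send surveys that are both de-identified and attached to a named sheet.

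**Each assurance tested against the cover-sheet workflow**

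1. *Vinfen staff see no responses.* They handle an unsealed survey with the name attached. The text says they look at the cover sheet; it does not say they read the answers. The assurance has no protection behind it but is not contradicted outright.
2. *Provider organizations have no access.* Vinfen is listed in Research Design and Methods among the six organizations operating the homes, and group home staff handle completed surveys on the mailing route. Again nothing prevents access, and nothing shows it occurs.
3. *Names are not collected.* The name is on the cover sheet and on the log, and both go to Vinfen. The statement carries no qualifier such as collection by MGH only. It is untrue for these residents.
4. *Identities are known only within the recruiting organization.* Vinfen's research staff check names on surveys from all participating homes. They also verify the preprinted name lists before distribution and track guardian consent. This statement does not fit the consent process, with or without the cover sheet.

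**Scope**

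Research Design and Methods anticipates about 1,400 residents with SMI and 800 with ID/DD: 1,400 + 800 = 2,200. That is a ceiling for each of the two waves (baseline and 12 months). The paper share is not stated. For illustration, with full response and an assumed share of 25% to 75%, the range is 0.25 × 2,200 = 550 to 0.75 × 2,200 = 1,650 per wave. True numbers would be lower, because residents without a required guardian consent and those judged unable to take part are excluded. The documents also do not say when the cover-sheet procedure began, and this protocol version is dated April 2022, so its application at baseline is not established.

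**The case against.** The strongest reply is that this is a wording conflict with no demonstrated harm. The name is on a removable sheet, MGH receives a de-identified survey, and the check serves a real purpose: keeping out surveys completed without the required guardian consent. Vinfen's community research staff have a research role distinct from resident care. Mailing by group home staff is the fallback route, and those staff are trained on autonomy and confidentiality. For this questionnaire the protocol names discomfort with the questions, not confidentiality, as the major risk. The fact sheet itself is not among the documents, and another part of Research Design and Methods describes a narrower promise about published reports and about confidentiality with agency and state leadership.

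Much of this stands. A reader might infer that staff read residents' answers, or that confidentiality has been breached; no text says so. A reader might also infer that answers are distorted more in TBP homes, because coaches may be present while residents complete the form. The documents do not say whether coaches attend GBP homes, and they give no evidence of greater pressure in either arm. Nor is any trial conclusion shown to be at risk: the Needs Assessment is not a listed primary or secondary outcome, and the co-primary outcomes come from agency infection data and program director surveys.

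The reply does not remove the conflict. Two descriptions of one step disagree, and the participant statement in Consent Procedures is unqualified. The consent check needs the name, but it does not need the name attached to unsealed answers.

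**Conclusion.** The point holds as an internal contradiction in participant protection. The resident paper workflow in Consent Procedures is incompatible with the de-identified workflow in Research Design and Recruitment, and it makes the statement that names are not collected untrue. The assurances that Vinfen and the providers do not see responses are unprotected, not disproved.

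Its reach is every resident who answers on paper under the cover-sheet procedure: an unknown number, at most about 2,200 per wave. Guarded answering is a reasonable inference without a size. The co-primary analyses and the power statements are untouched. The conclusion rests on the protocol text alone and assumes that the fact sheet follows the statement in Consent Procedures. It is worth correcting because it concerns the protocol's own primary risk and the remedy is cheap.

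**What to change.** Reconcile the Needs Assessment text in Research Design and Methods, the paper-questionnaire text in Recruitment Procedures, the participant statement in Consent Procedures and the identity statement in Privacy and Confidentiality with the resident paper workflow.

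- **Workflow.** Print only the study ID on the survey. On completion it is sealed in an inner envelope, and the name stays on a detachable outer cover or envelope. Vinfen's research staff check consent from the outer name, then either forward the inner envelope unopened or discard it unopened if consent is missing. The protocol already uses sealed envelopes for the log and for guardians' remuneration and consent forms, so this extends existing practice.
- **Participant statement.** Correct it in either case, because the name still reaches Vinfen on the outer cover and the log. It should say that community research staff use names to verify consent and that names are removed before responses reach the MGH researchers.
- **Privacy statement.** Acknowledge that Vinfen's research staff check names across organizations.

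The seal gives the protection, not the study ID, since the providers supply the IDs and hold the keys. A person helping a resident may still see the answers, which envelopes cannot prevent. The cost is envelopes, slightly more packing for each home, and an amendment to the protocol and instruction sheet. The consent check is kept.
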